5.2. SAMPLE SIZE AND POWER ESTIMATES

Aim 1: A sample size of 100 infants per group is sufficient to detect a 20% change in a parameter related to an outcome using standard parametric or nonparametric tests (e.g. Wilcoxon signed-rank) at 80% power, α =0.05, with expected standard deviation of change of 50%. We plan to enroll 120 to account for attrition due to early death. Statistical power of 80% for detecting 20% difference in parameters is maintained even if the incidence of outcome (e.g. BPD) is only 20% of enrolled (24 of 120) infants if the standard deviation is 40% or less (as is expected to be, based on preliminary studies).

Aim 2: A sample size of 16 infants is sufficient to detect a 30% change in a parameter related to an outcome using standard parametric (e.g. paired t-test) or nonparametric tests at 80% power, α =0.05, with expected standard deviation of change of 40%. Hence, enrollment of 25 patients will be sufficient, even if there is attrition of up to 5 patients due to death, and data from 4 patients has technical issues with usability.

Aim 3: As in Aim 2, 16 infants are sufficient to detect a 30% change in a parameter related to an outcome by standard parametric (e.g. paired t-test) or nonparametric tests at 80% power, α =0.05, with expected standard deviation of 40%. Hence, enrollment of 25 patients will enable detection of even minimal changes, or of changes in parameters with much variation.

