4.1. STUDY POPULATION

4.1.1. Inclusion Criteria

This study will enroll 120 neonates in our Regional NICU (RNICU) at UAB as follows:

- 1. Inborn infants weighing 401-1,000 grams on admission and/or 22^{0/7} to 28^{6/7} (<29 weeks) inclusive completed weeks of gestation,
- 2. Infants eligible for full care and resuscitation as necessary, and surviving beyond 24 h of age
- 3. Enrollment at <1 week post-natal age
- 4. Informed consent from parent/guardian

Aim 2: This study will enroll the subset of infants from Aim 1 who are still intubated or on nasal IMV at 2 weeks postnatal age, meet blood gas criteria (arterial or capillary arterialized blood gas values done q12-24h, as most infants do not have an arterial line at 2 weeks: pH > 7.25, $PaCO_2 > 40$ mm Hg), have $TcCO_2$ monitoring with $TcCO_2$ values that trend and correlate appropriately with $PaCO_2$, and are not judged too unstable by the Attending neonatologist.

Aim 3: This study will enroll the subset of infants from Aim 1 who are receiving oxygen supplementation at 32w and 36w PMA, and are not judged too unstable by the Attending neonatologist.

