4.3. POTENTIAL RISKS AND BENEFITS TO SUBJECTS

Potential Risks:

This study is primarily an observational study (Aim 1), and comparative effectiveness research (Aims 2 and 3), and is hence of low risk. Infants enrolled in this study are intrinsically at high risk, as they are born extremely preterm with a risk of death exceeding 20% and death or disability exceeding 50%, but participation in this study adds only minimally to the underlying risk.

For Aim 1, we will collect physiologic data from patient monitors, and clinical data on patient characteristics, illness severity, and outcomes from the medical records of the 120 enrolled infants. The primary risks are those of loss of confidentiality and privacy. Results and their linked clinical data will then be assigned an unique identifying code and anonymized to minimize risks to confidentiality. Only the PI and research coordinator will have access to patient data before anonymization. No patient identifiers will therefore remain in the data set that will be transmitted to the Data Coordinating Center.

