5.1. STATISTICAL ANALYSIS PLAN

It should include a plan for analysis of primary and secondary outcomes, subgroup analyses if planned, and for handling of missing data and subjects who die or are lost to follow-up.

Primary Outcome:

Hypoxemic episode (SpO2 <85% for >10s) frequency

Secondary Outcome(s)

Frequency of Hypoxemia (SpO₂<85%), Bradycardia (HR<100/min), Bradycardia episode (HR<100/min for \geq 10s); Apnea (RR=0 for >20s, or RR=0 for \geq 10s + SpO2 <85% or HR<100/min); BPD defined using physiologic definition at 36w PMA

Aim 1: Statistical calculations will be performed using SPSS. Parametric tests will be used for analyses of all continuous variables except for comparisons involving the incidences of specified ranges of IBIs, which is a skew distribution. Nonparametric tests will also be used for analyses of ordinal datasets. The Kolmogorov-Smirnov (one-sample) and Friedman's and Wilcoxon signed-rank tests will be used for the nonparametric analyses. For factorial analyses of parametric data, separate repeated-measures ANOVAs will be used. For factors with more than two levels, the Greenhouse-Geisser correction will be used, and ε with unadjusted degrees of freedom will be reported. Where a main effect was observed for factors with more than two levels, post hoc tests using the Bonferroni adjustment will be done. Values will be expressed as means and SD, and *p* values (2-tailed) of <0.05 considered statistically significant. Pearson product-moment correlation coefficient analysis will be used to establish the association between pathological pauses in breathing and breathing stability.

Aims 2 and 3: As in Aim 1, we will quantify IBI and IBI variability as defined earlier (2, 4). Also as in Aim 1, other outcomes will include (i) hypoxemic time –the % time with $SpO_2 <90\%$, (ii) moderate hypoxemic time with $SpO_2 <80\%$ and severe hypoxemic time with $SpO_2 <60\%$ (iii) bradycardic time – % time with HR <100, (iv) severe bradycardic time – % time with HR <60, (iv) hypoxemic, bradycardic, or apneic episodes – the number of episodes of $SpO_2 <90\%$, $SpO_2 <80\%$, $SpO_2 <60\%$, HR<100, HR<60, or RR=0, respectively, for >10 seconds, with the episode length defined as the number of seconds of data values below the threshold, (v) cerebral hypoxemic episodes (decrease in $r_cSO_2 <50\%$ or of 20% from baseline for >1 minute) and somatic hypoxemic episodes (decrease of 20% from baseline in peri-renal area).

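### Aim 1 enrols 120 to keep 100 after early death (a 16.7% allowance), but section 4.3 puts the death risk of enrolled infants above 20%, which leaves about 96 or fewer survivors

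*Combined protocol and SAP*

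**What the plan says.** All references are to the combined protocol and SAP.

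- **Section 5.2, Aim 1, size:** "A sample size of 100 infants per group is sufficient to detect a 20% change in a parameter related to an outcome". The inputs given are an SD of 50% for the change, a 5% significance level and power of 80%. The choice of test is left open, and the signed-rank test is named as an example. Section 5.1 sets two-sided testing: "values (2-tailed) of <0.05 considered statistically significant".
- **Section 5.2, Aim 1, allowance:** "We plan to enroll 120 to account for attrition due to early death". No other source of loss is mentioned for this aim. The next sentence claims that 80% power is kept if an outcome such as BPD occurs in 20% of those enrolled, given as 24 of 120, with SD at most 40%.
- **Section 4.3:** "Infants enrolled in this study are intrinsically at high risk, as they are born extremely preterm with a risk of death exceeding 20" per cent. No time window and no upper figure are given.
- **Section 4.1.1:** eligibility includes "Infants eligible for full care and resuscitation as necessary, and surviving beyond 24 h of age", with enrolment in the first postnatal week.
- **Section 5.2, Aim 2:** 25 infants are said to be enough even with up to 5 deaths and if "data from 4 patients has technical issues with usability".
- **Sections 5.3 and 5.4:** cost limits the sample to 120, although some further enrolment in early Year 5 is left open.

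**The concern.** The Aim 1 allowance covers death alone, and it is smaller than the only death risk that the protocol states for these infants. Aim 2 budgets 5 deaths in 25 (20%) among infants selected at 2 weeks of age, and Aim 1 budgets 16.7% from the first week. The difference is not explained.

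The BPD sentence in section 5.2 compounds this. It takes 20% of all 120 enrolled, although physiologic BPD is assessed at 36 weeks PMA and needs a surviving infant. Adjacent sentences therefore treat 100 and then 120 as the number available for analysis.

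What is at stake is the evaluable number. It is the figure against which retention will be judged, and the figure at which power should be quoted.

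**Working it through.** **1. Reproduce the plan's 100.** Inputs from sections 5.1 and 5.2: change 20%, SD 50%, so d = 20/50 = 0.4; two-sided α = 0.05; power 80%.

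- Two independent groups: n per group = 2 × (1.960 + 0.842)² × (50/20)² ≈ 98.1, so 99. The t-test version gives 99.1, so 100 per group, with power 80.4%.
- Paired: n = (1.960 + 0.842)² × (50/20)² ≈ 49.1, so 50. The t-test version gives 51.01, so 52. A signed-rank test (relative efficiency 0.955) needs about 54.

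The figure of 100 reproduces only as a per-group size for two independent groups, although the test named as an example is a paired one.

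**2. The allowance.** (120 − 100)/120 = 16.7%. The 120 also equals 100 × 1.20. That is what results if 20% is added to the target instead of dividing the target by the proportion retained: 100/(1 − 0.20) = 125.

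**3. Survivors from 120.** Section 4.3 gives only a lower bound of 20%. The 25% and 30% rows are assumptions that show the range.

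| Death risk after enrolment | Expected survivors of 120 | Probability of at least 100 survivors | Enrolment needed to expect 100 |
|---|---|---|---|
| 16.7% (implied by 5.2) | 100 | 56% | 120 |
| 20% (floor in 4.3) | 96 | 21% | 125 |
| 25% (assumed) | 90 | 2% | 134 |
| 30% (assumed) | 84 | under 0.1% | 143 |

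**4. Effect on power of 96 in place of 100 (d = 0.4).**

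- 100 read as per group: 80.4% falls to 78.7%.
- 100 read as the total, paired within infant: 97.7% falls to 97.3%. The detectable change at 80% power moves from 14.1% to 14.4%.
- 100 read as the total, split into two equal groups: 50.8% falls to 49.2%.

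Each fall is under 2 points.

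**5. The BPD sentence.** 20% of 96 is 19.2, so about 19 infants with BPD and 77 without, rather than 24 and 96. As a two-group t-test with d = 20/40 = 0.5, power is 58.4% for 24 v 96, 50.8% for 20 v 80 (100 survivors) and 49.2% for 19.2 v 76.8 (96 survivors). Most of the fall comes from deaths that the preceding sentence of 5.2 already expects; the step from 100 to 96 adds 1.6 points. The claimed 80% is not reached even with no deaths.

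**6. Unusable recordings, as a sensitivity only.** If Aim 2's 4 in 25 (16%) applied to Aim 1, 96 × 0.84 = 80.6, about 81. On the paired reading the detectable change would then be 15.8%.

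**The case against.** The strongest reply is that the two percentages may not measure the same thing. Section 5.2 speaks of early death without defining it. Section 4.3 gives an undated background risk in a passage about harms, explained by the infants' prematurity at birth. Infants who die in the first 24 hours are never enrolled, and some enrol several days later. If 20% is the risk from birth, 100 survivors are still expected once 4 percentage points of it fall before enrolment: 0.80/0.96 = 0.833 = 100/120. At 25% from birth, 10 points would have to fall there. This stands in part. The sentence in 4.3 is about enrolled infants and no other rate is offered for Aim 1, but the documents do not settle the timing.

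Two further replies also stand. An infant who dies after 2 weeks still contributes recordings to the prediction of hypoxemic episodes, which is Aim 1's primary hypothesis, so the shortfall concerns only outcomes that need survival. And Aim 2's 4 unusable recordings are a contingency for a single 96-hour recording. Aim 1 has three such recordings, sleep studies and sampled continuous data, so one technical failure need not remove an infant.

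A reader might infer that 120 enrolled cannot deliver 100, or that only about 80 usable infants should be expected. The documents support neither. Even at exactly 20% mortality there is a 21% chance of 100 or more survivors, and nothing in the plan makes 16% an expected rate of data loss for Aim 1.

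**Conclusion.** The point holds as a minor correction. On the only death risk stated for enrolled infants, 120 leave about 96 or fewer expected survivors rather than 100, and 20% of those is about 19 infants with BPD rather than 24. This assumes that the 4.3 figure applies after enrolment and up to the assessment, which the text suggests but does not say.

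It would be wrong to conclude that mortality leaves Aim 1 underpowered. The death shortfall costs 1.7 points per group or 0.5 points paired. If 100 means per group, 120 in total cannot supply two such groups even with no deaths. If the comparison is within infant, about 52 suffice and 96 is ample. The per-group ambiguity is thus the larger weakness in 5.2, and it does not depend on mortality; it has to be resolved before any power figure can be requoted.

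**What to change.** In section 5.2, Aim 1:

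1. Replace the implied 100 with the number expected to be evaluable from 120 at the assessments that need survival: about 96 or fewer at the 4.3 rate. Alternatively, state the post-enrolment death rate that justifies 100, define early death, and reconcile both with 4.3.
2. Say whether 100 is per group or in total and whether the comparison is within infant or between groups, and requote power or detectable change for that design at the revised number.
3. Base the BPD example on survivors (about 19 of 96) and requote its power.
4. If loss from unusable data is shown, label it as a sensitivity (about 81 if Aim 2's contingency applied).

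The cost is a few sentences of text and slightly less favourable figures. No extra enrolment is needed, and the 120 set by cost in section 5.3 can stay.

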3.2. SECONDARY HYPOTHESIS OR QUESTIONS (S) (IF APPLICABLE)

Aim 1: We hypothesize that mathematical models of personalized ventilatory patterns based on multiparametric vital signs monitoring and signal analysis methods will be able to predict (a) bradycardia events, (b) hypoxemic time, (c) bradycardia time, (d) apneic episodes in individual infants before they occur,

Aim 1: We hypothesize that mathematical models of personalized ventilatory patterns based on multiparametric vital signs monitoring and signal analysis methods will be able to identify patterns of ventilatory abnormalities associated with BPD with and without pulmonary hypertension, as well as with and without respiratory or feeding support at 3 months corrected age.

Aim 2: We hypothesize that late (at or beyond postnatal day 14) mild permissive hypercapnia is associated with reduction in (a) bradycardia events, (b) hypoxemic time, (c) bradycardia time, (d) apneic episodes

Aim 3: We hypothesize that servo-controlled oxygen environment is associated with reduction in (a) bradycardia events, (b) hypoxemic time, (c) bradycardia time, (d) apneic episodes

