4.2.4. Study Intervention and Comparison

Aim 1:

This is a non-interventional observational study, in which we will use the data from the intensive multiparametric physiologic monitoring of 96 hour duration at each of the three time points of 2 weeks postnatal age, 32 weeks PMA, and 36 weeks PMA as well as the polysomnography at 36w PMA and 3 months follow-up for this Aim. In addition, we will use a random sampling (3 continuous h/day of 2 days (Mon/Thurs) in each week of the infant's hospital stay) of the continuous data recording of HR, RR, and SpO₂ from enrollment to discharge. These data will be combined with clinical data during the hospital course as well as during follow-up, specifically data on respiratory or feeding support.

Data used will include HR, RR, SpO₂, ventilator/O₂ supplementation, $P_{ET}CO_2$ (end tidal CO₂ by microcapnography), T_CCO_2 (transcutaneous CO₂), r_cSO_2 (near-infrared cerebral oximetry), r_sSO_2 (near-infrared somatic oximetry), and temperature. Data acquisition, band-pass filtering, and wavelet transforms of the signals will be done as described (2, 4, 6, 29).

We will develop mathematical models of ventilatory patterns to predict apneic, hypoxemic and/or bradycardic episodes in individual infants before they occur. We will quantify the irregularity in breathing using the IBI and IBI variability as defined earlier (2, 4). The normal IBI is around 1 second, but due to the irregular breathing pattern in preterm infants, this may vary from <1s to 20s or longer. For this study, we will define eupnea as IBI <2s and apneic range as IBI>5s as done previously (29). The basic assumptions of the point process model for breathing are that peak inspiration (maximal inspiratory effort as recorded non-invasively) is a discrete event marked by neuronal inspiratory burst and that IBI dynamics are governed by multiple feedback and feed-forward loops modulating the respiratory oscillator. In addition to the respiratory signal, we will develop models using the ECG and SpO₂ signals plus respiratory signals to determine if accuracy is improved. We have developed point process models for the evaluation of bradycardia and its severity.

Aim 2:

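### With one value per infant, the Aim 1 claim of 80% power when 24 of 120 infants have the outcome works out at about 58%, and the 100-per-group figure does not match the within-infant test named with it

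*Combined protocol and SAP*

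**What the plan says.** Section 5.2 makes two power statements for Aim 1.

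- The first is "A sample size of 100 infants per group is sufficient to detect a 20% change in a parameter related to an outcome", at 80% power and α = 0.05, "with expected standard deviation of change of 50" percent. The Wilcoxon signed-rank test is given as an example. The section continues: "We plan to enroll 120 to account for attrition due to early death".
- The second is "Statistical power of 80% for detecting 20% difference in parameters is maintained even if the incidence of outcome (e.g. BPD) is only 20" percent of enrolled infants (24 of 120), on condition that the SD is 40% or less, which is said to be expected from preliminary studies.

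Section 5.1 sets the significance rule for Aim 1: p "values (2-tailed) of <0.05 considered statistically significant". On rank methods it says that the one-sample Kolmogorov-Smirnov, Friedman's and "Wilcoxon signed-rank tests will be used for the nonparametric analyses".

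The comparison that the second statement serves is in section 3.2: the models "will be able to identify patterns of ventilatory abnormalities associated with BPD with and without pulmonary hypertension". The data are to be collected "at each of the three time points of 2 weeks postnatal age, 32 weeks PMA, and 36 weeks PMA" (section 4.2.4), with sampled continuous recordings through the hospital stay.

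**The concern.** The second statement gives every input needed to check it. A 20% difference at an SD of 40% is half a standard deviation, and 24 infants in the smaller group looked too few to detect that with 80% power.

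The first statement combines a sample size for two independent groups with a test and an SD that belong to change within the same infant. Two groups of 100 also cannot be formed from 120 infants.

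At stake is how a negative BPD comparison would be read. If readers believe the study had 80% power when it had less than 60%, they will take a null result as stronger evidence of no difference than it is.

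**Working it through.** **Inputs.** Difference 20%, SD 40%, 24 of 120 infants with the outcome and α = 0.05 (section 5.2); two-sided testing (section 5.1). The 96 infants without the outcome follow from 120 − 24. One value per infant is assumed.

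**Formulas (noncentral t).**
- Two groups: d = difference/SD, δ = d·√(n₁n₂/(n₁+n₂)), df = n₁+n₂−2.
- Within infant: δ = d·√n, df = n−1.
- Power = P(|T| > t₀.₉₇₅) for noncentral t with parameter δ.

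**Step 1: the section's other figures.**
- Aim 2: d = 30/40 = 0.75; the paired t-test needs n = 15.98, which is the stated 16.
- Aim 1, 100 per group: d = 20/50 = 0.4; the two-sample t-test needs 99.1 per group, and 100 per group gives 80.4%.

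Both reproduce with ordinary two-sided t calculations.

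**Step 2: the 24-of-120 statement.** d = 20/40 = 0.5. δ = 0.5 × √(24 × 96/120) = 0.5 × √19.2 = 2.191, df = 118, critical value 1.980. Power = **58.4%**. The normal approximation agrees: Φ(2.191 − 1.960) = 59.1%.

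**Step 3: other splits and readings at d = 0.5.**

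| Reading | Power |
|---|---|
| 24 vs 96 | 58.4% |
| 24 vs 76 (100 evaluable, losses only among infants without the outcome) | 56.1% |
| 24 vs 72 (96 evaluable, same pattern of loss) | 55.6% |
| 20 vs 80 (100 evaluable, 20% incidence) | 50.8% |
| 36 vs 84 (30% incidence) | 70.2% |
| 48 vs 72 (40% incidence) | about 76% |
| 60 vs 60 (best split of 120) | 77.5% |
| Within-infant test on the 24 alone | 65.0% |

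The nearest any reading comes to 80% is 78.9%: a one-sided within-infant test on the 24, by normal approximation. That contradicts the two-tailed rule and does not compare infants with and without BPD.

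**Step 4: what would give 80%.**
- 24 vs 96: a difference of 25.8% at SD 40%, or an SD of at most 31.0% for a 20% difference.
- 24 vs 76: 26.5%, or an SD of at most 30.2%.
- At 20% incidence and SD 40%: about 199 infants in total (198.2 before rounding up).

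**Step 5: the first statement read as within-infant.** At d = 0.4 the paired t-test needs 51.01 infants, so 52; 100 infants give 97.7%.

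**Step 6: averaging three windows (assumption).** If 40% is the single-window SD and ρ the correlation between windows in the same infant, the SD of the mean is 40% × √((1+2ρ)/3). At 24 vs 96, power is 80.1% at ρ = 0.4, 75.8% at 0.5, 64.6% at 0.8 and 58.4% at 1.0.

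**Step 7: Aim 3.** Section 5.2 says 25 infants can show even very small changes. With a paired test at its SD of 40%, the change detectable at 80% power is 23.4% with all 25 evaluable and 30.0% with 16.

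**The case against.** The best defence is that section 5.2 never says each infant contributes a single value. Averaging the three monitoring windows would restore 80% if the within-infant correlation were about 0.40 or lower. The routine recordings sampled throughout the stay could supply more windows: with 10 the threshold rises to about 0.56, and with 24 to about 0.58 (both counts are assumptions). Adjusting for a baseline covariate correlated at about 0.63 with the parameter would have a similar effect. These routes are real, so the 58% is conditional. But the plan states no averaging, no correlation and no covariate, and the preliminary data behind the 40% are not shown. A power claim that depends on such an assumption has to state it.

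Four smaller points also have weight.

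- The signed-rank test is only an example, and 100 evaluable infants out of 120 is a natural reading of the first statement. On that reading the number is more than adequate and only *per group* is wrong.
- Section 5.1 applies parametric tests to most continuous variables, which could include a two-group comparison. What is missing is a named test, and a rank test for independent groups where the data are skewed or ordinal.
- The 120 is not an absolute ceiling. Section 5.3 attributes it to cost, but section 5.4 allows some further enrolment in early Year 5.
- The claim covers any SD up to 40%. Power is 70% at 35% and reaches 80% at about 31%, so the statement fails only between about 31% and 40%, but it asserts 80% there too.

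**Conclusion.** The concern holds. On the plan's stated inputs, with one value per infant and a two-sided test, the 80% is about 58%, and lower after early deaths. The shortfall is more than 20 percentage points at the SD limit the plan itself sets. It is not a difference of method, because the section's other figures reproduce and this one does not.

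The 100-per-group statement is inconsistently described rather than underpowered on every reading: as two groups it needs about 200 infants, and as a within-infant test it is ample.

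The consequence is limited to a secondary Aim 1 comparison in the plan's own low-incidence case. The primary Aim 1 hypothesis, predicting hypoxemic episodes in individual infants, is untouched. The Aim 3 wording is a minor overstatement.

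**What to change.** Restate section 5.2, using one evaluable number for each calculation.

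- **Outcome-group comparison (two-sample t-test or rank-sum).** Either assume all 120 are evaluable (24 vs 96): about 58% power for a 20% difference at SD 40%, and 80% power for about 26%. Or assume 100 evaluable, the plan's allowance for early death (24 vs 76): about 56%, and 80% power for about 27%. If deaths also fall among infants who would have had the outcome, recompute with the smaller group reduced.
- **Within-infant change (paired t-test or signed-rank).** State that 100 infants give about 98% power for a 20% change at an SD of change of 50%, and delete *per group*.
- **Repeated windows.** If the 80% was meant to rest on averaging, give the number of windows, the assumed within-infant correlation, and whether the 40% is a single-window or averaged SD.
- **Section 5.1.** Name the two-sample test and its rank-based counterpart for comparing infants with and without the outcome.
- **Aim 3.** Replace the claim about very small changes with a detectable change of about 23% if all 25 infants are evaluable.

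The cost is wording in section 5.2 and one added analysis in section 5.1. No extra infants, visits or measurements are needed; the stated power for the BPD comparison becomes less favourable.

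### Aim 3's claim that 25 infants can detect minimal changes does not follow from its own inputs, which give a detectable change of about 23%

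*Combined protocol and SAP*

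**What the plan says.** Section 5.2 of the combined protocol and SAP gives Aim 3 a short power statement modelled on Aim 2. It opens: "As in Aim 2, 16 infants are sufficient to detect a 30% change in a parameter related to an outcome". Power is put at 80% and alpha at 0.05, with the paired t-test as the example and nonparametric tests as the alternative. The variability input is worded "with expected standard deviation of 40" per cent. From this the section infers that "enrollment of 25 patients will enable detection of even minimal changes, or of changes in parameters with much variation". It gives no detectable change for 25 infants and no allowance for losses.

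Aim 2, in the same section, uses the same 16 infants, 30% change, power, alpha and enrolment of 25, but describes its input as "with expected standard deviation of change of 40" per cent. It uses its surplus of nine infants differently, covering up to five deaths and four unusable recordings.

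Sidedness is given only in the Aim 1 paragraph of Section 5.1: "values (2-tailed) of <0.05 considered statistically significant".

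**The concern.** The closing sentence is worded as a consequence of the figures before it, so a reader will take it as a calculated property of the design. Raising the number of infants from 16 to 25 improves the detectable change only with the square root of the sample size, that is by a factor of about the square root of 16/25, or 0.8. A 30% detectable change cannot become a minimal one that way.

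Aim 3 is a randomised cross-over comparison of two ways of giving oxygen, and the background in Section 3.3 says that a difference between them would matter clinically. If the comparison shows no significant difference, a protocol that claims sensitivity to minimal changes invites the reading that small differences have been excluded. The design could not exclude them.

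**Working it through.** **Inputs**

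- Change 30%, standard deviation 40%, power 80%, alpha 0.05, 16 infants, enrolment 25: Section 5.2, Aim 3.
- The 40% is the standard deviation of the paired difference: stated under Aim 2 and taken to carry over to Aim 3.
- Two-sided test: stated under Aim 1 in Section 5.1 and assumed for Aim 3.
- One paired difference per infant and all 25 infants evaluable: assumed.

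**Method**

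For a paired t-test on n infants with true mean change δ and standard deviation of change s, the test statistic has a noncentral t distribution with n − 1 degrees of freedom and noncentrality λ = (δ/s)·√n. Power is the probability that it falls beyond ±t(0.975, n − 1).

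**Step 1: reproduce the plan's figure**

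- n = 16: λ = (30/40)·√16 = 3.00, critical value 2.131, power 80.06%.
- n = 15: power 77.1%.

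So 16 is the smallest number that reaches 80%, and the plan's figure reproduces with 40% as the standard deviation of change.

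**Step 2: detectable change with 25 infants**

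With 24 degrees of freedom the critical value is 2.064, and 80% power needs λ = 2.920. Hence δ = 2.920 × 40/√25 = **23.4%**. The normal approximation gives (1.960 + 0.842) × 40/5 = 22.4%. A one-sided test would give 20.5%.

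**Step 3: power of 25 infants for smaller changes**

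| True change | λ = (δ/40) × 5 | Power |
|---|---|---|
| 5% | 0.625 | 9% |
| 10% | 1.25 | 22% |
| 15% | 1.875 | 44% |
| 20% | 2.5 | 67% |
| 30% | 3.75 | 95% |

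For 80% power, a 10% change would need 128 infants and a 5% change 505.

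**Step 4: the claim about variable parameters**

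Hold the change at 30% and solve for the largest standard deviation that keeps 80% power with 25 infants: s = 30 × 5/2.920 = **51.4%**. The margin over 40% is about 11 percentage points.

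**Step 5: fewer evaluable infants**

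The detectable change is 26.4% with 20 evaluable infants and 30.0% with 16.

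**Step 6: the nonparametric alternative**

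Simulating the Wilcoxon signed-rank test with its exact null distribution and normally distributed differences (mean 0.75 standard deviations) gives power of 76.8% at n = 16, 79.8% at n = 17 and about 94% at n = 25. The 80% stated for 16 infants therefore holds for the paired t-test and is slightly too high for the signed-rank test.

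**The case against.** The best defence is that the sentence is a loose closing remark. The enrolment target, the test and the design all stand without it, and 25 infants give 95% power for the 30% change that the section sizes for. That is right, and it limits the point to wording. It does not rescue the sentence, which is offered as a deduction from stated inputs and fails as one. How a null result would in practice be read is a matter of judgement, since the documents do not say.

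Four stronger readings are tempting, and the documents do not support them.

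- **That Aim 3 uses the wrong standard deviation.** A reader might infer this because Aim 3 leaves out 'of change'. But the sentence refers back to Aim 2, repeats its inputs, and yields 16 infants exactly when 40% is the standard deviation of change. If 40% were a per-period figure, the standard deviation of change would be 40·√(2(1 − ρ)). The stated 16 would then reproduce at a within-infant correlation ρ of 0.5, but not at 0.25 (23 infants) or 0.75 (10 infants). The documents give no ρ. Two omitted words are the likelier explanation. The 23% figure itself depends on this reading, so the two criticisms cannot be made together.
- **That Aim 3 is underpowered.** For a 30% change it is not.
- **That Aim 3 will lose nine infants, as Aim 2 allows for.** Aim 2's allowance includes deaths among infants studied from two weeks of age, whereas Aim 3 studies infants at 32 and 36 weeks postmenstrual age. Its losses may be smaller. The plan simply gives no figure.
- **That the signed-rank shortfall threatens the aim.** It is about three percentage points at 16 infants, depends on the assumed normal differences, and no longer matters at 25.

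**Conclusion.** The concern holds for the closing sentence of the Aim 3 power statement. On the plan's own inputs, 25 evaluable infants detect a change of about 23% with 80% power. They have a 22% chance of detecting a 10% change and a 9% chance of detecting a 5% change. The accompanying claim about highly variable parameters amounts to tolerance of a standard deviation of about 51% in place of 40%, for a 30% change only.

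This rests on 40% being the standard deviation of within-infant change, a two-sided alpha of 0.05, one paired difference per infant and no losses. Relaxing sidedness moves the detectable change to 20.5%, and losses move it up towards 30%. None of these makes it minimal. The missing words 'of change' are an ambiguity to clear up and do not show a wrong input. The signed-rank figure is a secondary correction.

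**What to change.** In Section 5.2, Aim 3:

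1. Add 'of change' after 'standard deviation', to match Aim 2.
2. Delete the closing claim about minimal changes and highly variable parameters, and put in its place: *With an expected standard deviation of within-infant change of 40% and a two-sided alpha of 0.05, 25 evaluable infants give 80% power by paired t-test to detect a change of about 23% (about 26% if 20 are evaluable, 30% if 16).* Giving all three figures shows the effect of losses without having to assume a rate.
3. For Aims 2 and 3, tie the 80% power at 16 infants to the paired t-test. If the nonparametric test is kept in the sentence, say that the signed-rank test has about 77% power at 16 infants and about 80% at 17, under normally distributed differences.

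The cost is editorial. Enrolment, design and analysis stay as they are. The one disadvantage for the sponsor is that a stated sensitivity becomes less favourable.
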